#### 12.2.3.1 Diagnosis of CRPS

Diagnosis of CRPS according to the clinical diagnostic criteria in [Table 4](#) must be documented at the Enrollment Visit upon examination of the subject. It is the absolute responsibility of the investigator to make the diagnosis of CRPS according to the correct diagnostic criteria. Application of the CRPS diagnostic criteria requires identification of an affected limb. Distal to mid-limb involvement (especially hand or foot), with or without proximal spread, should be present. Evidence of asymmetrical signs and symptoms, relative to the contralateral (less affected) limb, is a requirement for fulfilling the diagnostic criteria. A precise location of the CRPS, consistent with the location of signs and symptoms, must be documented in the CRF. If more than 1 limb is considered to be affected, the trial-designated CRPS most affected-limb must be readily distinguished based on asymmetrical signs and symptoms, relative to the contralateral limb, and the subject must be able to differentiate pain in the affected limb from pain in any other affected limbs. **Diagnosis of CRPS involving an atypical body part (e.g., trunk, breasts, pelvic regions, lower back, face) is not permitted for this trial.**

Table 4: Complex regional pain syndrome clinical diagnostic criteria recommended by the IASP; “Budapest clinical criteria”

- 
1. Continuing pain, which is disproportionate to any inciting event.
  2. Must report at least one symptom in *three of the four* following categories:
    - Sensory: reports of hyperesthesia and/or allodynia.
    - Vasomotor: reports of temperature asymmetry and/or skin color changes and/or skin color asymmetry.
    - Sudomotor/edema: reports of edema and/or sweating changes and/or sweating asymmetry.
    - Motor/trophic: reports of decreased range of motion and/or motor dysfunction (weakness, tremor, dystonia) and/or trophic changes (hair, nail, skin).
  3. Must display at least one sign at time of evaluation in *two or more* of the following categories:
    - Sensory: evidence of hyperalgesia (to pinprick) and/or allodynia (to light touch and/or deep somatic pressure and/or joint movement).
    - Vasomotor: evidence of temperature asymmetry and/or skin color changes and/or asymmetry.
    - Sudomotor/edema: evidence of edema and/or sweating changes and/or sweating asymmetry.

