    - Motor/trophic: evidence of decreased range of motion and/or motor dysfunction (weakness, tremor, dystonia) and/or trophic changes (hair, nail, skin).
  4. There is no other diagnosis that better explains the signs and symptoms.
- 

IASP = International Association for the Study of Pain

Source: Harden et al. 2010a

In accordance with procedures for validation of these criteria, symptoms will be assessed with a recall period “since the onset of CRPS”. Signs must be present, i.e., observed by the examiner, during the evaluation at the Enrollment Visit.

Subjects will be examined for 8 signs (observed on examination, yes or no): hyperalgesia to pinprick; allodynia (light touch, deep joint pressure, vibration, cold, and heat); temperature asymmetry by palpation (affected side cooler or warmer than the contralateral side); skin color asymmetry (red, blue or pale, mottled, or scar); asymmetric edema; sweating asymmetry (increased or decreased on the affected side); dystrophic changes nails, hair, or skin); and motor changes (tremor, dystonia, decreased active range of motion, or weakness) (see Section 18.4).

Medical history related to CRPS must include the following: date and description of precipitating event (e.g., type of trauma, surgery; if no precipitating event is known, document as unknown), the specific location of CRPS, including the affected limb (if more than 1 limb is affected, the most painful limb as well as any other affected limb must be identified), the date of onset of symptoms, and date of CRPS diagnosis. Any documentation supporting the diagnosis of CRPS, including any assessments used to rule out alternative diagnoses, will be retained.

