#### **12.4.8 CRPS Severity Score**

Signs and symptoms of CRPS (Section 18.4) will be assessed by the investigator at Visit 2 (baseline) and Visit 7 through Visit 11 and recorded using the electronic patient reported outcome system. Subjects will be queried on 8 self-reported symptoms (queried yes or no): allodynia and/or hyperalgesia; temperature asymmetry; skin color asymmetry; sweating asymmetry; asymmetric edema; dystrophic changes; motor changes; and decreased active range of motion. Symptoms will be assessed based on a recall period of 48 hours. Subjects will be examined for 8 signs (observed on examination, yes or no): hyperalgesia to pinprick; allodynia; temperature asymmetry by palpation; skin color asymmetry; sweating asymmetry; asymmetric edema; dystrophic changes; and motor

changes. Each sign or symptom is assigned a dichotomous value (1 = presence; 0 = absence). The resulting score ranges from 0 to 16, with higher scores indicating greater CRPS severity (Harden et al. 2010b).

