### **13.3.6 Complex Regional Pain Syndrome Severity Score**

Signs and symptoms of CRPS will be assessed by the investigator at Visit 1 (enrollment), at Visit 2 (baseline) and Visit 7 through Visit 11 and recorded using the electronic patient reported outcome system.

The investigator examines the signs. The subjects are asked to report their symptoms with a recall period of 48 hours. At the Enrollment Visit, subjects are additionally asked to report their symptoms with a recall period since onset of disease for purposes of establishing the diagnosis of CRPS. This information is also used, in combination with the investigators assessment of signs of CRPS at

Visits 9, 10 and 11, to determine whether or not the subject continues to meet criteria for a diagnosis of CRPS at these latter visits ([Table 2](#)).

Table 2: Assessments of CRPS signs and symptoms

	Enrollment	Baseline	Post-baseline
	Visit 1	Visit 2	Visit 7 – Visit 11
Symptoms (recall period since onset) a	X		(X c )
Symptoms (recall period 48 hours) b	X	X	X
Signs	X	X	X

a) Used for establishing the diagnosis of CRPS.

b) Used for CRPS severity score.

c) Values copied from Visit 1.

CRPS = complex regional pain syndrome.

Subjects will be queried on 8 self-reported symptoms (queried YES or NO):

1. Continuing, disproportionate pain.
2. Allodynia and/or hyperalgesia.
3. Temperature asymmetry.
4. Skin color asymmetry.
5. Sweating asymmetry.
6. Edema.
7. Dystrophic changes.
8. Motor abnormalities.

Moreover, subjects will be examined for 8 signs (observed on examination, queried YES or NO):

9. Hyperalgesia to pinprick.
10. Allodynia.
11. Temperature asymmetry by palpation.
12. Skin color asymmetry.
13. Asymmetric edema.
14. Sweating asymmetry.
15. Dystrophic changes.
16. Motor abnormalities.

Each sign or symptom is assigned a dichotomous value (1 = YES/presence; 0 = NO/absence). To derive the CRPS severity score, the symptoms reported with recall period 48 hours and the signs will be added. The resulting CRPS severity score ranges from 0 to 16. If the value for 1 of the

16 signs and symptoms is missing, the CRPS severity score will not be calculated and is considered missing.

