The presence of CRPS at post-baseline Visits 7 to Visit 11 will be derived based on the “Budapest clinical diagnostic criteria” (Harden et al. 2010). For the Budapest criteria to be fulfilled, 3 criteria must be verified. The criteria are linked to the symptoms with recall period since onset and the signs in the following way:

1. Criterion (1): question 1 answered YES
2. Criterion (2): at least 3 of the following 4 symptom categories must be fulfilled:
  - Sensory: question 2 answered YES
  - Vasomotor: question 3 or question 4 answered YES
  - Sudomotor/edema: question 5 or question 6 answered YES
  - Motor/trophic: question 7 or question 8 answered YES
3. Criterion (3): at least 2 of the following 4 sign categories must be fulfilled
  - Sensory: question 9 or question 10 answered YES
  - Vasomotor: question 11 or question 12 answered YES
  - Sudomotor/edema: question 13 or question 14 answered YES
  - Motor/trophic: question 15 or question 16 answered YES

A subject data listing will present for:

- The individual signs and symptoms values (YES/NO).
- The answers to follow-up questions in case a sign or symptom is present.
- The CRPS severity score.
- The presence/absence of CRPS (Visits 7 through Visit 11).
- Comments.

A descriptive summary will be created by sign/symptom and visit for:

- The dichotomous symptoms and signs,
- The dichotomous CRPS assessment (present/absent).

For the Enrollment Visit, symptoms with recall period since onset and symptoms with recall period 48 hours will both be summarized. A graphical display of the proportion of affected subjects over the entire 12-month trial period will be created including:

- The proportion of subjects with a sign/symptom, for each of the symptoms with recall period 48 hours and for each of the signs.
- The proportion of subjects meeting the diagnosis of CRPS, i.e., with CRPS presence.

Furthermore, a descriptive summary of the continuous CRPS severity score and the corresponding change from baseline will be generated by visit. A graphical plot of the means and 95% CI of the CRPS severity score over the entire 12-month trial period will be created.

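### CRPS presence at Visits 7-11 is judged by the sign rule that gated entry, with no derived Visit 2 value to show how much loss re-examination alone produces

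*SAP*

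**What the plan says.** **Entry.** Inclusion criterion 3 (Protocol 1.3.1) ties the diagnosis to Visit 1. Table 4 in Protocol 12.2.3.1 sets the sign requirement: "Must display at least one sign at time of evaluation in *two or more* of the following categories". The text below the table adds: "Signs must be present, i.e., observed by the examiner, during the evaluation at the Enrollment Visit".

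**Follow-up.** SAP 13.3.6 derives CRPS presence after baseline from three criteria. The third is "Criterion (3): at least 2 of the following 4 sign categories must be fulfilled". The first two use symptoms recalled since onset, and SAP Table 2 says these values are copied from Visit 1. Each visit stands alone, with no confirmation at a second visit.

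**Visit 2.** Protocol 12.4.8 says that signs and symptoms "will be assessed by the investigator at Visit 2 (baseline) and Visit 7 through Visit 11". Protocol 11.2 places treatment-period procedures before dosing unless otherwise indicated, so the Visit 2 signs are pre-dose. SAP 8.2.2 takes baseline generally as the Visit 2 value, and the CRPS severity score is reported as change from that baseline. CRPS presence has no Visit 2 value: it is derived and listed for Visits 7 to 11 only, and the since-onset row of SAP Table 2 is blank at Visit 2.

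**Display.** SAP 13.3.6 tabulates presence by visit and plots over 12 months "The proportion of subjects meeting the diagnosis of CRPS, i.e., with CRPS presence".

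**Visit list.** An earlier paragraph of SAP 13.3.6 says the since-onset symptoms are combined with signs at "Visits 9, 10 and 11, to determine whether or not the subject continues to meet criteria for a diagnosis of CRPS". The derivation itself names Visits 7 to 11.

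**The concern.** Subjects enter because they were at or above a cut-off on one examination, and are then re-examined against the same cut-off. If sign detection is less than perfectly repeatable, some who passed at Visit 1 will fall below the line later with no change in disease. The implied starting point is 100%, so in this display re-examination error can only lower the proportion.

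A declining curve over 12 months invites the reading that subjects stopped meeting the diagnosis after neridronic acid. There is no comparator arm to show how much of the decline would have happened anyway. The Visit 2 examination is the one pre-treatment repeat that did not gate entry. It could show the re-examination component directly, and the SAP does not use it for this outcome.

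**Working it through.** The documents give no expected loss of diagnosis, no distribution of sign categories at entry and no examiner reliability, so there is no planned figure to reproduce. Every rate below rests on assumptions. The only inputs from the documents are the 2-of-4 rule at Visit 1 and at Visits 7-11, the fixed symptom criteria, and about 290 planned subjects.

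**1. Simplest case.** Suppose each category shows a sign with the same probability p at every examination, independently and without change. Then

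P(absent) = P(fewer than 2 of 4) = (1-p)^4 + 4p(1-p)^3.

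For p = 0.7: 0.0081 + 0.0756 = 0.0837, and 290 x 0.0837 = 24.3 subjects.

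| p | Falsely absent at one visit | Of 290 |
|---|---|---|
| 0.95 | 0.05% | 0.1 |
| 0.9 | 0.4% | 1.1 |
| 0.8 | 2.7% | 7.9 |
| 0.7 | 8.4% | 24.3 |
| 0.6 | 17.9% | 52.0 |

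**2. Persistent differences between subjects.** A simulation of 400,000 subjects used lasting subject and category effects, independent visit noise, no trend, visit-to-visit kappa of about 0.15 to 0.60, and selection on at least 2 of 4 at Visit 1. Falsely absent at one later visit: 15-26% at category prevalence 50%, 10-17% at 60%, 6-9% at 70%, 3-4% at 80%, and under 1% at 90%.

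**3. True status with detection error.** Assume sensitivity and specificity of 0.9 per category and equal numbers of subjects with 2, 3 or 4 truly positive categories.

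- P(fewer than 2 observed) is 0.1557, 0.0253 and 0.0037 for 2, 3 and 4 true categories.
- The chance of passing at Visit 1 is the complement: 0.8443, 0.9747 and 0.9963, which sum to 2.8153.
- Falsely absent at one later visit: (0.8443 x 0.1557 + 0.9747 x 0.0253 + 0.9963 x 0.0037) / 2.8153 = 0.1598 / 2.8153 = 5.7%, or about 17 of 290.

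With the same error rates the result is 2.1% if most subjects have 4 true categories and 9.6% if most have 2. At sensitivity 0.7 with most subjects at 2 categories it reaches 30.0%, so 26% is not an upper bound.

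**4. What a Visit 2 value adds.** With no true change and independent errors, Visit 2 and any later visit are exchangeable given selection at Visit 1. The expected rate of absence at Visit 2 is therefore also 5.7% in step 3, and the expected difference between a later visit and Visit 2 is zero. In the simulation the Visit 2 and later rates agreed within 0.1 percentage point.

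**5. What restricting to Visit 2 positives does.** Limiting the denominator to subjects positive at both Visit 1 and Visit 2 selects above the line again. The weights in step 3 become the squares 0.7128, 0.9500 and 0.9926, which sum to 2.6555, and the false loss is 0.1387 / 2.6555 = 5.2%. Most of the 5.7% remains. The useful reference is the unrestricted Visit 2 proportion.

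**The case against.** **The stakes are low.** CRPS presence is not a secondary endpoint or other listed outcome in Protocol 1.2, nor among the parameters listed at the head of SAP 13.3. The listed CRPS outcome is change in the severity score, which has a Visit 2 baseline. All analyses are exploratory (Protocol 14.1.2), and Protocol 8.1 already urges caution without a comparator. This stands and makes the point minor.

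**The reference data are not lost.** Each sign is summarised by visit and plotted in the same display, and individual values are listed, so a general fall in signs between Visit 1 and Visit 2 would be visible. This also stands. What is missing is a derivation. Separate sign curves do not show how many subjects fall below 2 of 4 categories, however.

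**The effect may be negligible.** Each category can be met by either of two signs, and allodynia by any of several stimuli, so category prevalence may be high. At 90% the false loss is under 1%. Nothing in the documents rules this out.

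**The cut-off is simply the diagnostic rule.** Re-applying the same criteria is reasonable, and no other cut-off is proposed here.

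**Stronger readings.** A reader might infer that the planned curve will mostly show noise, or that it is biased overall towards remission. The documents support neither. They supply no reliability figure, and they speak of continuing to meet criteria, not of remission. Copying the Visit 1 symptoms pushes the other way, because resolved symptoms can never make a subject absent. A reader might also conclude that absence must be confirmed at two consecutive visits. That is a debatable choice: a first absence at Visit 11 could never be confirmed.

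**Conclusion.** The point holds as a minor one. Entry and follow-up share the 2-of-4 sign rule, signs alone decide the follow-up result, and no Visit 2 value is derived although the signs are collected. Some apparent loss of diagnosis from re-examination is to be expected whenever detection is imperfect. Its size rests wholly on assumed prevalence and reliability: under 1% to about 26% per visit over category prevalences of 50-90% and the kappa range used, and higher under harsher assumptions.

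A Visit 2 reference measures the part due to re-examination over the enrollment interval (up to 60 days). It does not remove slower natural change over 52 weeks, which a single-arm trial cannot separate from a drug effect. The consequence is confined to how one exploratory table and curve are read.

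**What to change.** In SAP 13.3.6:

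- Derive CRPS presence at Visit 2 as well, from the Visit 1 since-onset symptoms and the Visit 2 signs, with the same algorithm. Extend the since-onset row of SAP Table 2 to Visit 2.
- Include the Visit 2 value in the listing, the table and the plot, labelled as the pre-treatment reference.
- Compare the Visit 7-11 proportions with the Visit 2 proportion among all subjects, without restricting to those positive at Visit 2.
- Optionally add a count of subjects absent at two consecutive visits, as a supplementary description that does not redefine the outcome.
- Reconcile the mention of Visits 9, 10 and 11 with the derivation at Visits 7 to 11.

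The cost is a few lines of SAP text and one more derived visit, with no new data or subject burden. The apparent loss of diagnosis relative to the reference may be smaller. If few subjects are absent at Visit 2, later losses become more credible.

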## **14 ANALYSIS OF PHARMACOKINETIC AND PHARMACODYNAMICS PARAMETERS**

In the following sections, a detailed description of all calculations and statistical methods used in the analysis of pharmacokinetic and pharmacodynamic parameters is presented.

Descriptive and graphical methods will be used to summarize the trial results.

Summaries will be grouped by treatment and time of assessment.

Missing data will be treated as such and will not be imputed or replaced in any way if not specified otherwise.

### **14.1 Analysis of pharmacokinetic data**

Not applicable.

### **14.2 Analysis of pharmacodynamic data**

Pharmacodynamic data comprise bone turnover markers and data from bone densitometry and MRI procedures. The analysis of pharmacodynamic data is described in the following sections.

#### **14.2.1 Bone turnover markers**

Bone turnover markers will be analyzed in the Pharmacodynamic Set.

The following bone turnover markers are assessed at Visit 2 and at Visits 6, 7, 8, 9, 10, and 11:

- Bone formation markers:
  - Procollagen type I amino-terminal propeptide (PINP).
  - Bone alkaline phosphatase (BAP).
- Bone resorption marker:
  - C-terminal telopeptide of type I collagen (CTX).

All bone turnover marker data will be listed in a subject data listing.

Bone turnover marker values, including changes from baseline, will be descriptively summarized by time point.

A graphical plot of the mean and 95% CI of bone turnover marker values over time will be presented. Similarly, a plot of the mean change from baseline of bone turnover marker values over time will be presented.

#### **14.2.2 Bone densitometry and magnetic resonance imaging procedures**

Data collected in the electronic case report form (eCRF) will be listed for all subjects in the Bone Imaging Set. No further statistical analysis is planned in this SAP. Bone densitometry and MRI data will be analyzed and reported separately by a dedicated bone imaging service provider.

## 15 SAFETY ANALYSES

Safety data will be summarized descriptively overall, i.e., for the single treatment group neridronic acid 400 mg.

All safety data will be presented for the SAF unless otherwise specified.

### 15.1 Adverse events

All adverse events with start date/time after first IMP administration in a subject administered a trial treatment will be defined as treatment emergent adverse events (TEAE) irrespective of causal relationship.

A pre-treatment non-TEAEs is an adverse event starting in the pre-treatment period as defined in Section 8.2.2.

If there are partial dates or times, an adverse event will be considered treatment emergent unless the information available will clearly exclude it. Further details can be found in Section 20.1.6.1.

The causal relationship of TEAEs to IMP is categorized as follows:

Category	Assessment by investigator:
Related	certain probable/likely possible
Not related	unlikely not related
Unknown	unassessable/unclassifiable conditional/unclassified causal relationship is missing

A TEAE is considered to be ‘expected’ when the nature or intensity is consistent with the information in the neridronic acid investigator’s brochure. Otherwise, it is considered to be an ‘unexpected’ TEAE. Expectedness will be assessed by the sponsor.

The following overview tables will be generated overall, i.e., for the single treatment group neridronic acid 400 mg.

1. Summary of the number and percentage of subjects with at least 1:

- TEAE.
- Serious TEAE.
- Non-serious TEAE.
- Unexpected TEAE.
- Related TEAE.
- Related serious TEAEs.
- TEAE leading to discontinuation from IMP.
- TEAE leading to discontinuation from the trial.
- Deaths.

The percentage denominator will be the number of subjects.

2. Summary presenting the number of TEAEs per subject categorized as 0, 1, 2, 3, 4, 5, and >5.
3. Summary of the number and percentage of TEAEs for:
  - TEAEs.
  - Serious TEAEs.
  - Non-serious TEAEs.
  - Unexpected TEAE.
  - Related TEAEs.
  - Related serious TEAEs.
  - TEAE leading to discontinuation from IMP.
  - TEAE leading to discontinuation from the trial.

The percentage denominator will be the total number of TEAEs.

If more than 10 subjects discontinue the trial/IMP due to TEAE, the incidence and the incidence rate of TEAEs leading to discontinuation from the trial/from IMP will be summarized by SOC and PT.

If more than 5% of the subjects discontinue the trial due to TEAE, the distribution of the time to discontinuation from trial due to TEAE will be summarized using time-to-event methods. Time will be days until discontinuation. The time to discontinuation will be censored at the End-of-Trial Visit or at the time point of discontinuation if not due to TEAE.

If more than 5% of the subjects permanently discontinue IMP due to TEAE, the distribution of the time to discontinuation from IMP due to TEAE will be summarized using time-to-event methods. Time will be days until discontinuation. The time to discontinuation will be censored at the last planned infusion visit (Visit 5), or at the time point of discontinuation, whichever occurs first.

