**Classification of causation**

The causal relationship of an adverse event to IMP will be classified using the following terminology. The given criteria for each term are for consideration and are neither exhaustive nor required to be fulfilled in total for the selection of the respective term:

Terms for classification of causation	Criteria for the selection of causality classification terms
Conditional/ Unclassified:	Additional data for a proper assessment are under examination.
Unassessable/ Unclassifiable:	The available data cannot be judged because information is insufficient or contradictory, and cannot be supplemented or verified.
Not related:	Data with sufficient evidence to accept that there is no causal relationship to IMP administration (i.e., there is no temporal relationship to IMP administration or proved other cause).
Unlikely:	Data without sufficient evidence to accept that there is no causal relationship to IMP administration, but also with no evidence or argument to suggest a causal relationship (e.g., the temporal relationship to IMP administration makes a causal relationship improbable, and other drugs, chemicals, or underlying disease[s] provide plausible explanations).
Possible:	Data with limited evidence or argument to suggest a causal relationship (e.g., there is a reasonable time sequence to administration of the drug, but the adverse event could also be explained by concurrent disease[s] or other drugs or chemicals. Information on drug withdrawal may be lacking or unclear).
Probable/likely:	Data with sufficient evidence or argument to suggest a causal relationship (e.g., there is a reasonable time sequence to administration of the drug, the adverse event is unlikely to be attributed to concurrent disease[s] or other drugs or chemicals, and a clinically reasonable response on withdrawal [dechallenge]).
Certain:	Data with clear evidence for a causal relationship (i.e., a clinical event, including laboratory test abnormality, occurs in a plausible time relationship to drug administration, and it cannot be explained by concurrent disease or other drugs or chemicals. The response to withdrawal of the drug [dechallenge] should be well defined and clinically plausible, using a satisfactory rechallenge procedure if appropriate).

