### **15.1.1 Incidence, incidence rates and number of events**

The incidence of an adverse event is defined as the number of subjects with occurrence of this adverse event during the period of interest.

The incidence rate (CIR for crude incidence rate) of an adverse event is defined as the number of subjects with occurrence of this adverse event during the period of interest divided by the total number of subjects  $n$  in the respective group (e.g., treatment group).

The incidence, incidence rate, the number of events and the percentage of events (related to the total number of events) will be summarized by PT sorted by decreasing incidence rate for:

- TEAEs.
- Serious TEAEs.
- Non-serious TEAEs.
- Related TEAEs.

A separate table per type of TEAE will be prepared. The tables will be restricted to events with an incidence rate of at least 5% ( $\geq 5\%$ ).

The incidence, incidence rate, the number of events and the percentage of events (related to the total number of events) will be summarized by SOC and PT (sorted alphabetically) for each:

- TEAEs.
- Serious TEAEs.
- Non-serious TEAEs.
- Related TEAEs.

For serious TEAEs, the incidence, the incidence rate, the number of events and the percentage of events will also be presented for serious related TEAEs, serious fatal TEAEs and serious fatal related TEAEs.

For all enrolled subjects, the incidence, incidence rate, the number of events and the percentage of events (related to the total number of events) will be summarized by SOC and PT (sorted alphabetically) for each:

- Pre-treatment non-TEAEs.
- Serious pre-treatment non-TEAEs.

Presentation will only be overall and not per treatment.

The number and percentage of events will be summarized by SOC and PT (sorted alphabetically) for the following TEAE descriptors. Presentation will be for TEAEs only.

- Intensity: mild, moderate, severe.
- Causal relationship to the IMP: related (with subcategories: possible, probable/likely, certain), not related (with subcategories: not related, unlikely), unknown (with subcategories: conditional/unclassified, unassessable/unclassifiable, causal relationship missing).
- Outcome: recovered/resolved, recovering/resolving, not recovered/not resolved, recovered/resolved with sequelae, fatal, unknown.
- Non IMP related countermeasures: none, newly started medication, trial discontinuation, others.
- Action taken with IMP: drug interrupted, drug withdrawn, not applicable, unknown.

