**20.1.1.7 Handling of missing values**

At each time point/visit, all subjects still in the trial are reported. Missing values will be taken into account as missing in the analysis. The number of observed values and the number of missing values must sum up to the number of subjects in the trial at the respective time point/visit.

Missing measurements/missing values are identified by the SDTM variable \*\*STAT=ND. If this variable is not recorded (it's a permissible variable) the missing values of \*\*ORRES should be used.

Unless otherwise specified in the SAP, missing values will not be imputed.

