#### **Handling of missing date information**

The term missing date/time refers to a completely missing date/time or to an incomplete date/time where parts are not available, e.g., missing hours.

If the number of adverse events with missing date information does not exceed 10% the following imputation strategy is applied.

Missing start and end date/times will be imputed conservatively, i.e., missing values will be imputed in such a way that the duration of the adverse event is considered with the longest possible duration and such that, whenever the adverse event may potentially start after first IMP administration, the adverse event will be handled as a TEAE.

I1-I4: imputation steps

C1-C4: checkpoints

Figure 2: Graphical overview about the imputation strategy

Further explanations on the flow chart:

The different steps of the displayed imputation strategy must be completed from the first to the last step. All procedures in each step must be completed in the order given.

- Imputation:

- I1: Impute with date/time of first IMP
- I2:
  - a) Impute with first calendar day and/or first calendar month.  
Imputation will be done based on the available partial information starting with month and then day. The respective first month and day will be chosen for imputation:

Missing date	Imputed date
2014-Mar	2014-Mar-01
2014	2014-Jan-01

- I2:
  - b) Impute with first hour and/or first minute.  
Imputation will be done based on the available partial information starting with hour and then minutes. The respective first hour of a day and first minute will be chosen for imputation. “00:00” will be considered as the first hour/ first minute per day.

Missing time	Imputed time
11:--	11:00
--:--	00:00

- I3: Impute with date/time of informed consent signed  
If signing of informed consent was not collected with time information set adverse event start time to 00:00.
- I4:
  - a) impute with last calendar day and/or calendar last month  
Imputation will be done based on the available partial information starting with month and then day. The respective last month and day will be chosen for imputation:

Missing date	Imputed data
2014-Mar	2014-Mar-31
2014	2014-Dec-31

For February, leap years must be taken into account when calculating the last day in February.

1.1. b: impute with last hour and/or last minute

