**Expression**

---

certain – probable/likely – possible – conditional/unclassified – unassessable/unclassifiable – unlikely – not related

---

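### TEAEs of unknown causality enter no Related count and are never tabulated by subject, so the related, related serious and serious fatal related incidences are lower bounds

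*SAP*

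**What the plan says.** SAP 15.1 (Adverse events) maps the investigator's causality terms to three categories. Related is "certain probable/likely possible". Not related is the two terms below that, unlikely and not related. Unknown is "unassessable/unclassifiable conditional/unclassified causal relationship is missing".

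The Related category then defines several outputs:

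- The overview tables in SAP 15.1 have rows for related and related serious TEAEs, once by subject and once by event. The subject table uses the number of subjects as its denominator.
- SAP 15.1.1 tabulates related TEAEs by PT and by SOC and PT. For serious TEAEs, the same measures "will also be presented for serious related TEAEs, serious fatal TEAEs and serious fatal related TEAEs".

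Unknown appears in one table, the causality descriptor table of SAP 15.1.1. There it has three subcategories by SOC and PT, the unit is the event, and the base is all TEAEs.

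The Protocol (12.3.1, Classification of causation) gives two of the unknown terms different meanings. For conditional, the entry reads "Additional data for a proper assessment are under examination". Unassessable is used when the information is insufficient or contradictory and cannot be completed or confirmed. SAP 20.1.1.7 sets the general rule: "Unless otherwise specified in the SAP, missing values will not be imputed". No exception is made for causality.

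**The concern.** A subject whose only serious TEAE has a pending, unjudgeable or missing causality entry stays in the denominator of the related serious row but cannot enter its numerator. No companion row shows that this subject exists. Compared with a count that includes the Unknown cases, the planned figure can only be equal or lower, so any uncertainty runs in one direction.

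This matters because the trial is single-arm and exists to describe safety for registration (Protocol 6.4 and 8.1). Without a comparator, investigator causality is a main route to any drug-related rate. Related serious and related fatal counts are likely to be small, and one case can then separate a statement of none from a statement of one.

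**Working it through.** **Reproducing a figure.** The documents state no related-TEAE rate and no expected number of unknown-causality events, so there is no plan figure to reproduce. The check has two parts: a trace of where Unknown goes, and an illustration of size.

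**Trace through the outputs**

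| Output (SAP section) | Unit | Is Unknown visible? |
|---|---|---|
| Any TEAE, primary endpoint (15.1, 15.5) | Subjects | Included; TEAE status ignores causality |
| All serious and all fatal TEAEs (15.1, 15.1.1) | Subjects and events | Included; causality not used |
| Related and related serious (15.1, 15.1.1) | Subjects and events | Excluded, no companion row |
| Serious fatal related (15.1.1) | Subjects and events | Excluded, no companion row |
| Causality descriptor table (15.1.1) | Events, all TEAEs | Own category; no subjects, no split by seriousness or fatal outcome |
| Listings of deaths and other SAEs (15.1.1) | Individual cases | By hand count only |

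**Size**

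Inputs:

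- N = 290, the planned approximate number (Protocol 1.5.1, SAP 5.2), taken here as the Safety Set size.
- r = subjects with a related TEAE of the given type (assumed values).
- u = subjects with an unknown-causality TEAE of that type and no related one of the same type (not given; assumed range 0 to 15).

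Formulas: planned rate = r/N; rate with Unknown added = (r + u)/N; gap = u/N. Per affected subject the gap is 1/290 = 0.34 percentage points.

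Exact (Clopper-Pearson) 95% limits are shown only to convey scale. SAP 15.1 and 15.1.1 plan no interval for TEAE incidence.

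| Type | r | u | (r + u)/290 | 95% limits |
|---|---|---|---|---|
| Serious fatal related | 0 | 0 | 0% | 0 to 1.26% |
| | 0 | 1 | 0.34% | 0.01 to 1.91% |
| | 0 | 3 | 1.03% | 0.21 to 2.99% |
| Related serious | 3 | 0 | 1.03% | 0.21 to 2.99% |
| | 3 | 1 | 1.38% | 0.38 to 3.49% |
| | 3 | 3 | 2.07% | 0.76 to 4.45% |
| Any related | 145 | 0 | 50.0% | 44.1 to 55.9% |
| | 145 | 3 | 51.0% | 45.1 to 56.9% |
| | 145 | 15 | 55.2% | 49.3 to 61.0% |

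The gap is small for any related TEAE. For rare types it is small in percentage points but large relative to the count: with 3 related and 1 unknown, the planned figure is 3/4 of the combined one. With u = 0 nothing changes.

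**The case against.** The other side has a good case, and much of it stands.

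- **No data show understatement.** A reader might infer that the related rates will be understated. The documents do not support that. Understatement needs unknown-causality events to remain at lock, to be truly drug-related, and to fall in subjects with no related event of the same type. None of this is documented.
- **Many cases may resolve.** Causality is a CRF field for every adverse event, the first SAE notification asks for the investigator's assessment, the investigator signs the CRF as complete, and the final analysis follows hard lock (SAP 6.1). This also undercuts the idea that serious events are the most prone to unknown causality, for which the documents offer no evidence. The answer is partial, however. Only the conditional term means pending. The Protocol's definition of unassessable describes information that cannot be supplemented, and the SAP plans all three unknown subcategories, including missing, in its final tables.
- **Unknown is not hidden.** It is a category of its own, it is not merged with Not related, and the individual serious and fatal cases can be found in the listings. That is correct, but a hand count from listings is not a tabulated incidence.
- **No internal contradiction.** A reader might take the worst-first order in SAP 20.1.6.1, "certain – probable/likely – possible – conditional/unclassified – unassessable/unclassifiable – unlikely – not related", as showing that Unknown ought to count as Related. It sets a presentation order only, and it places both unknown terms below possible, the lowest Related term, which agrees with SAP 15.1. Likewise "Missing start and end date/times will be imputed conservatively" concerns the dates of adverse events and hence TEAE status, not causality.
- **Recoding Unknown as Related is debatable.** It would give a related event count in the overview that disagrees with the three-way descriptor table, and it would label as related what the investigator said could not be judged. This stands, and the fix below avoids it.

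**Conclusion.** The point holds as one about lower bounds and missing subject-level reporting. The related, related serious and serious fatal related incidences leave out every TEAE with unassessable, conditional or missing causality, and no planned table lets a reader see how many subjects, or how many serious or fatal cases, this concerns.

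The size is 0.34 percentage points per affected subject. This rests on a Safety Set of 290 and on the subject having no related event of the same type. It is zero if no unknown-causality events remain at lock. The counts in the illustration are assumptions, not forecasts. The primary endpoint and the all-causality serious and fatal summaries do not change. This is a cheap improvement to the reporting of a single-arm safety trial, not a flaw in its main result.

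**What to change.** In SAP 15.1 and 15.1.1, keep the strict Related definition and the three-way causality table by event. Beside each related, related serious and serious fatal related TEAE row, add a subject-level row for related or unknown, meaning subjects with at least one TEAE of that type whose causality falls in either category. The reader then has a lower and an upper figure on the same denominator, and the two related event counts stay consistent.

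The cost is a sentence of SAP wording and a few extra table rows, with no new data collection. The upper figure may look slightly less favourable than the strict one.
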